2.1 Primary objective

- The primary objective of this study is to compare clinical outcomes at two years following surgery between FA TKA and MA TKA. The primary outcome measure for this study is the Forgotten Joint Score (FJS) at two years after surgery. The null hypothesis is that there is no difference in functional scores at two years following surgery between patients undergoing MA TKA (control group) versus FA TKA (investigation group). The hypothesis is that outcome measures obtained at two years after surgery in patients undergoing FA TKA are not achievable using MA TKA. Further PROMs will be used to further assess clinical outcomes including Forgotten Joint Score (FJS), Oxford Knee Score (OKS), Knee injury and osteoarthritis outcome Junior score (KOOS Jr), VAS Pain, and Kujala scores preoperatively and postoperatively at 3 months, 1 year and 2 years. Also health-related quality of life will be measured using European Quality of Life questionnaire with 5 dimensions for adults (EQ-5D-5L) preoperatively and postoperatively at 3 months, 1 year and 2 years. Range of movement (degrees) in knee joint during inpatient admission and postoperatively at 6 weeks, 3 months, 1 year and 2 years.

2.2 Secondary objectives The secondary objectives of the study are:

- Determine lower limb alignment achieved with both alignment techniques. Lower limb alignment as assessed using standing long leg x-rays performed postoperatively at 3 months. Measurements of the hip-knee-angle (HKA), medial proximal tibial angle (MPTA) and lateral distal femoral angle (LDFA). Also evidence of imbalance with implant lift off will be measured.

- Determine if there are any differences in analgesic requirements based on alignment method used. Analgesia requirements during inpatient admission and postoperatively at 6 weeks, 3 months, 1 year and 2 years will be measured.
- Determine whether alignment method utilized has an effect on the sagittal stability of the TKA. Assessment of sagittal stability at Preop, 3 months, 1 year and 2 years will be undertaken with an arthrometer “Lachmeter”.
- Determine whether alignment method utilized has an effect on functional outcomes. This will be assessed by a combination of
 - Maximum voluntary isometric force using a hand-held dynamometer at Preop, 3 months, 1 year and 2 years.
 - Sit to stand values as measure of function at Preop, 3 months, 1 year and 2 years.

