3.10 Clinical and radiological assessment

The FJS, EQ5D-5L, OKS, VAS Pain, Likert scale, KOOS Jr and Kujala Anterior knee pain scores are validated tools for the clinical assessment of patients after knee arthroplasty (10,11,18,19). Each of these scores is completed preoperatively and then at regular intervals during follow-up (Appendix 19.1). This information is routinely discussed at each of these outpatient consultations but patients in this study will have the information recorded within these validated questionnaires to facilitate data analysis.

Routine clinical measures of height, weight, range of movement and pain description will be taken. To test endurance and strength, a 30 sec Sit to stand test will be measured. This test asks the participant to stand up / sit down from a standardised chair height within 30 seconds (Appendix 19.6). To measure the AP stability of the knee (20), a lachmeter reading will also be recorded at the post operative intervals and to measure strength, a hand

held dynamometer test will also be performed.

	Preoperative	Discharge	6 weeks	3 months	1 year	2 years
Patient demographics	X					
Patient medical history	X					
Operation details		X				
Clinical history and PROMS (FJS, EQ5D-5L, OKS, VAS pain, KOOS Jr, Kujala Anterior Knee Pain, Likert scale)	X		X (FJS and VAS only)	X	X	X
Functional Examination (Lachmeter testing, Range of Movement, Hand Held Dynamometer, 30s STS test)	X	X (range only)	X (range only)	X	X	X
Adverse Events	At occurrences through study period					

Table 1. Timelines for clinical data collection in all study patients.

	Preoperative	Discharge	6 weeks	3 months	1 year	2 years
Plain knee joint radiographs	X	X			X	X
Plain long-leg radiographs	X			X		
CT Knee joint	X					

Table 2. Timelines for radiological data collection in all study patients. Assessment windows will be as followed; 6 weeks review (± 1 week), 3 month review (± 2 weeks), 12 month review (± 2 months), 2 year review (± 2 months).

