4.2 Patient withdrawal criteria and procedure

All patients included into this study are free to withdraw from the study at any time without compromise to their future treatment. On withdrawal, patients will revert to the standard follow-up regimen for routine TKAs at the study site. The end of study form will be completed and the reason for withdrawal documented (Appendix 19.2). This form will also be completed if the patient is lost to follow-up or dies during the course of the study.

Enrolled patients will be withdrawn from the study if:

- The patient withdraws consent for participation in the study
- The patient is no longer able to comply with study instructions, attend scheduled appointments or complete questionnaires
- The patient undergoes implant revision

Data to the point of withdrawal will be used for analysis.

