6.0 Statistical Methods

6.1 Power / Sample size calculation

Primary Outcome measure: Functional outcome as assessed using the FJS score at two years following Mako-arm assisted TKA.

Using data from our initial cohort recording functional outcomes, the mean FJS score at 1 year in the mFA TKA was 59 (SD 6) and in the kFA TKA was 75 (SD 8). It is assumed that MA results will be no better than mFA results. The study was powered to demonstrate a 12 point difference in the Forgotten Joint score, which is the minimal clinical important change in the score. Using a one tailed analysis (assuming superior results with the kFA), an alpha value of 0.05 and power of 0.80, and accounting for expected drop-out rate of 10%, this study will need 100 patients to answer the study question.

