6.2 Endpoint Analysis

6.2.1 Primary Endpoint

The analysis of the per-protocol population will be considered the primary analysis. The differences

between the MA TKA and FA TKA groups will be analysed by calculating the difference from baseline, per patient, and a two-sided confidence interval for the difference between the changes from baseline will be calculated. This confidence interval will cover the true difference in the percentage change from baseline with a probability of 95%.

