6.4 Per-protocol population

The per-protocol population is defined as all patients who are randomised to MA TKA or FA TKA and complete the study according to the protocol.

In the event that there are errors in the randomisation assignment, the analysis will be performed using the treatment that the patient actually received, not the assigned treatment. Patients will be considered protocol violators if they do not meet the eligibility criteria as outlined in the protocol. Other reasons to be considered a protocol violator include, but are not limited to, protocol violations, and any actions that compromise the effectiveness of the treatment, such as receiving a secondary treatment. Protocol violators will not be considered as part of the per-protocol population and will be listed separately with the reason for their exclusion from the per-protocol population.

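### The per-protocol change-score analysis leaves the earlier FJS scores of patients who drop out with no way into the primary comparison

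*Combined protocol and SAP*

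**What the plan says.** - **Outcome (section 2.1).** "The primary outcome measure for this study is the Forgotten Joint Score (FJS) at two years after surgery". The same section lists the FJS among the questionnaires that run to "Kujala scores preoperatively and postoperatively at 3 months, 1 year and 2 years".
- **Schedule (section 3.10, Table 1).** A 6-week collection is added: "X (FJS and VAS only"). The visit forms in Appendix 19.1 agree. A patient who leaves after the 1-year visit can thus have three postoperative FJS scores.
- **Primary method (section 6.2.1).** The arms "will be analysed by calculating the difference from baseline, per patient, and a two-sided confidence interval" for the difference between the arms' changes is then calculated. The section names no visit, repeated-measures model, covariate or missing-data rule. Two years is the natural reading from sections 2.1 and 6.1.
- **Primary population (sections 6.2.1 and 6.4).** "The analysis of the per-protocol population will be considered the primary analysis", and that population is "all patients who are randomised to MA TKA or FA TKA and complete the study according to the protocol".
- **Withdrawal (section 4.2).** "Data to the point of withdrawal will be used for analysis". Which analysis is meant is not said. Implant revision is one of the listed reasons for withdrawal.
- **Imputation (section 6.3).** Patients who stop early stay in the intention-to-treat population and are handled by univariate or multivariate imputation. The model and its predictors are not given.
- **Expected loss (section 6.1).** The sample size is set "accounting for expected drop-out rate of 10" per cent.

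**The concern.** Two barriers act together. A patient without a 2-year FJS has no 2-year change to calculate, and a patient who does not complete the study is outside the primary population. Scores already collected from that patient at 6 weeks, 3 months and 1 year are therefore set aside in the primary comparison.

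An analysis of completers estimates the difference among all randomised patients only if leaving is unrelated to outcome, or related to it in a way that cancels between arms. Here leaving may track the state of the knee. Section 4.2 withdraws patients at implant revision and patients who can no longer attend or complete questionnaires, and section 14.2 links early revision to infection, instability and severe pain. The earlier FJS scores are the best evidence in the trial on whether leavers were doing badly. If such patients leave more often from one arm, the completer comparison is shifted in favour of that arm, although data that could correct much of the shift are on file.

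**Working it through.** **The plan's own figures.** Section 3.5 needs 90 completers, 45 per arm. Allowing for 10% drop-out, 90 / 0.9 = 100, which matches the target. About 10 patients are thus expected to lack a 2-year score.

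**Standard deviation.** No SD is given for the 2-year FJS or for its change from baseline. The 1-year cohort SDs of 6 and 8 do not lead to 45 per arm: with a 12-point difference, one-sided 0.05 and 80% power they need only 4 to 6 per arm. That is a separate matter. For this check I assume the SD that the plan's 45 per arm implies:

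SD = 12 / [(1.645 + 0.842) × √(2/45)] = 22.9

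The standard error with 45 per arm is then 22.9 × √(2/45) = 4.83.

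**Correlation.** The correlation r between 1-year and 2-year FJS is not in the documents. I assume 0.5 to 0.8.

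**Precision under random drop-out, 10% in each arm.** The variance using the 1-year score of leavers, relative to completers only, is

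[(1 − r²)/45 + r²/50] / (1/45)

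| r | Variance ratio | SE ratio | Effective n per arm | Power, one-sided |
|---|---|---|---|---|
| completers only | 1 | 1 | 45 | 80.0% |
| 0.5 | 0.975 | 0.987 | 46.2 | 80.9% |
| 0.7 | 0.951 | 0.975 | 47.3 | 81.7% |
| 0.8 | 0.936 | 0.967 | 48.1 | 82.3% |

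The standard error falls by about 1–3%.

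**Bias under drop-out related to the 1-year score.** This was simulated with 50 per arm, all drop-out after the 1-year visit, and the log-odds of leaving rising by 1 for each SD of lower 1-year FJS. The completer difference was compared with the likelihood (regression) estimate that uses the 1-year score.

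| Drop-out | Completer bias at r = 0.5, 0.7, 0.8 (FJS points) | Likelihood estimate |
|---|---|---|
| 10% v 10%, related | about 0 at each r | bias about 0, SE almost the same |
| 15% v 5%, related | about 1.0, 1.4, 1.6 | bias below 0.1 |

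Separate runs agreed to within about 0.1 to 0.2 points. Against the 12-point target, 1.0/12 = 8% and 1.6/12 = 13%. Against the standard error, 1.0/4.83 = 0.2 and 1.6/4.83 = 0.3.

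**Limits of the simulation.** It models 2-year means, not changes from baseline. Drop-out depends only on the observed 1-year score, so the likelihood estimate is close to unbiased by construction.

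**The case against.** **Missing data are not ignored.** Section 6.3 keeps early leavers in the intention-to-treat set, imputes for them, and commits to pursuing follow-up after a patient exits. Some leavers may therefore have a 2-year FJS, and a multivariate imputation could use the earlier scores. This stands. A reader might infer that the earlier scores would be lost whichever population were primary. The documents do not support that: with the intention-to-treat set primary, an imputed 2-year value would give these patients a change score. What remains is that this route is not primary and that its predictors are unstated. A univariate method need not use the earlier FJS at all.

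**Section 4.2 is not broken.** A reader might take its sentence as a promise about the primary analysis. It names no analysis, and imputation in the intention-to-treat set or the 3-month and 1-year summaries could satisfy it. The fault is that sections 4.2, 6.2.1, 6.3 and 6.4 are not reconciled.

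**The population matters as much as the method.** This also stands. A repeated-measures model fitted to the per-protocol set would still leave out patients who withdraw.

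**The gain is small.** Largely true. Outcome-related drop-out at the planned 10% in both arms does no visible harm in the simulation. The bias needs drop-out that differs by arm, and nothing in the documents predicts 15% versus 5%.

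**Conclusion.** The concern holds in a limited form. As written, the primary analysis cannot use postoperative FJS scores from patients who do not complete the study, because the change score and the per-protocol definition both shut them out. The cost in precision is about 1–3% of the standard error at the planned drop-out.

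The stronger reason to act is protection against unequal, outcome-related drop-out, worth about 1 to 1.6 FJS points in the 15% versus 5% case and about nothing when drop-out is equal. A reader might infer that drop-out related to outcome is enough by itself to bias the result; the 10% versus 10% case shows that it is not.

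These sizes rest on an assumed SD of 22.9, an assumed correlation of 0.5 to 0.8, and drop-out after the 1-year visit. That the earlier scores have no route into the primary comparison rests on none of them. It does take 2 years as the visit meant in section 6.2.1.

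**What to change.** **Change to section 6.2.1.** Make the primary analysis a mixed model for repeated measures of FJS at 6 weeks, 3 months, 1 year and 2 years, with arm, visit, arm-by-visit and baseline FJS-by-visit terms and an unstructured covariance. Include every patient with at least one postoperative FJS, in the arm to which the patient was randomised. Report the arm difference at 2 years with its two-sided 95% confidence interval as the primary result, and keep the per-protocol completer comparison as a sensitivity analysis. Model and population have to change together.

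**Alternative.** Multiple imputation in all randomised patients, with the earlier FJS scores named as predictors, is acceptable and stays closer to section 6.3.

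**Consistency.** State in section 4.2 which analyses use data collected before withdrawal, and align sections 6.3 and 6.4 with that.

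**Cost.** Analysis-plan wording and some programming; no new visits, patients or measurements. The model assumes that drop-out is explained by the FJS scores observed before it. That is weaker than what the completer analysis assumes, but it may fail for patients withdrawn at implant revision, so a prespecified sensitivity analysis for those patients is needed.

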1.2 Need for a trial

There is a need for high quality evidence on the clinical and radiological benefits of functionally aligned TKA. This study would show if there is any superior outcomes to be obtained from functional alignment. Clinical and functional outcomes should also be correlated to longer-term outcomes to better establish the “safe zone” for functional alignment.

Currently the vast majority of TKA throughout the world is undertaken utilizing MA alignment. Any change to a newer technique from the current ‘gold standard’ would need to be justified by improved clinical outcomes as there is no long term longevity data for Functional Alignment. Both surgeons and patients are only able to consider the relative risks and benefits of this technique once they are defined by sound scientific evidence. This study will contribute to the body of this evidence.

2. Objectives

The overall aims of this prospective, randomised double-blinded controlled trial are to compare functional, clinical, and radiological outcomes in FA TKA versus MA TKA. Patients undergoing MA TKA will form the control group and those undergoing FA TKA will form the investigation group. A superiority design will be used to evaluate whether FA TKA provides superior outcomes compared to MA TKA. Primary and secondary objectives will be used to quantify and draw inferences on differences in the efficacy of treatment between the two groups. To ensure accuracy of planning and implantation robotic arm assisted surgery will be utilized in both groups (Stryker MAKO, Fort Lauderdale, FL). Standardised post-operative care will be undertaken to ensure the only difference between groups is alignment of implants.

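### Section 6.2.1 computes a confidence interval for a difference in FJS points but says it covers the difference in percentage change with 95% probability, which is false in general

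*Combined protocol and SAP*

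**What the plan says.** Section 6.2.1 is the plan's only description of the primary analysis. It specifies "calculating the difference from baseline, per patient, and a two-sided confidence interval for the difference between the changes from baseline". The next sentence attaches a coverage property to that same interval: "This confidence interval will cover the true difference in the percentage change from baseline with a probability of 95" per cent. The section names neither the instrument, the unit nor the time point.

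The rest of the plan works on the score itself:

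- Section 2.1: "The primary outcome measure for this study is the Forgotten Joint Score (FJS) at two years after surgery".
- Section 2.1, hypothesis: "The null hypothesis is that there is no difference in functional scores at two years following surgery".
- Section 6.1: "The study was powered to demonstrate a 12 point difference in the Forgotten Joint score". The same section describes 12 points as the smallest clinically important change.

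Percentage change from baseline is not defined or used anywhere else.

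**The concern.** An interval built for one parameter is credited with 95% coverage of another. A difference in mean change is in points. A difference in percentage change also depends on where patients start. The two agree only in special cases, such as no treatment effect with equal baselines.

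Three things are at stake:

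- The primary analysis is given a property it does not have, and the shortfall grows with the true effect. It is worst when the trial finds a difference of the size it was powered for.
- The reporting scale is left open. An analyst could defend reporting either points or percentages, and could choose after seeing the data.
- A percentage result could not be read against the 12-point difference used for powering. It would also be undefined for any patient with a preoperative score of zero.

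**Working it through.** **Inputs from the documents.** Completers per arm: 45 (Section 3.5). Powering difference: 12 points, one-tailed alpha 0.05, power 0.80 (Section 6.1). Initial-cohort FJS at one year: mean 59, SD 6, and mean 75, SD 8 (Section 6.1), a difference of 75 − 59 = 16 points. Stated coverage: 95% (Section 6.2.1).

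**Assumptions.** The documents give no baseline FJS, so I take a common baseline *b* of 30, 40 or 50 for every patient. The SD of change then equals the SD of the follow-up score. I use SD 8 (the larger stated value) and SD 22.7. The latter is not a documented SD; it is the value at which 45 per arm gives 80% one-sided power for 12 points.

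**Step 1: the two scales.** If the arms' two-year means are y1 and y0, with y1 − y0 = d, then

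100(y1 − b)/b − 100(y0 − b)/b = 100d/b.

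This equals d only if d = 0 or b = 100. For d = 12 it is 40, 30 and 24 percentage points at b = 30, 40 and 50.

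**Step 2: width of the interval.** SE = SD × √(2/45), which is 1.687 (SD 8) or 4.786 (SD 22.7). With t(0.975, 88 df) = 1.987, the half-widths are 3.35 and 9.51 points. A trial that observed exactly 12 points would report about 8.65 to 15.35 or 2.49 to 21.51. Neither interval contains 24, 30 or 40.

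**Step 3: coverage.** For the points difference, coverage is 95% by construction, so the plan's figure is reproduced on that scale. For the percentage figure, coverage is P(|T| ≤ 1.987), where T is noncentral t with 88 df and noncentrality (d − 100d/b)/SE.

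Chance (%) that the nominal 95% points interval contains the percentage difference:

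| True d (points) | SD 8, b = 30 / 40 / 50 | SD 22.7, b = 30 / 40 / 50 |
|---|---|---|
| 0 | 95 / 95 / 95 | 95 / 95 / 95 |
| 2 | 21.9 / 57.9 / 78.4 | 83.9 / 90.5 / 93.0 |
| 4 | 0.02 / 6.0 / 35.0 | 51.2 / 76.4 / 86.9 |
| 8 | 0 / 0 / 0.3 | 2.9 / 30.2 / 62.0 |
| 12 | 0 / 0 / 0 | 0.01 / 3.9 / 30.2 |
| 16 | 0 / 0 / 0 | 0 / 0.1 / 8.9 |

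**Step 4: baselines that vary between patients.** An independent simulation used 20,000 trials per setting, 45 per arm, mean baseline 10 to 50, correlation 0.3, follow-up SD 8 or 22.9, and a true difference of about 11 to 12 points. (22.9 is the normal-approximation counterpart of 22.7.) Coverage of the points difference was 94.8% to 95.3% in every scenario. Coverage of the difference in mean percentage change was 0% for mean baselines 10 to 30, 0% to 0.8% at 40, and 0.01% to 20% at 50. Defining percentage change from the group means instead raised it to at most 28%. With no effect and equal baselines, coverage was about 95% on either scale.

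**Step 5: would baseline adjustment help?** Mean 95% half-width at SD 22.7, from 6,000 simulated trials per setting:

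| Baseline SD ÷ follow-up SD | Correlation | Change score | ANCOVA | Trials with ANCOVA wider |
|---|---|---|---|---|
| 1 | 0.5 | 9.49 | 8.27 | 0% |
| 0.5 | 0.2 | 9.72 | 9.35 | 10% |
| 0.5 | 0.5 | 8.20 | 8.25 | 79% |

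The documents give neither the baseline SD nor the correlation, so the gain from ANCOVA could be useful or nil. At SD 8, one-sided power for 12 points is at least 0.9996 even for the change score with equal SDs and zero correlation, so the choice has no power consequence there.

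**The case against.** The best defence is that this is one misplaced word. The first sentence fixes the procedure and the second only describes it. Delete the word and a valid 95% interval remains, with no change to any computation. Randomisation makes baselines equal in expectation, so whether the interval excludes zero keeps its error rate; type I error and power are untouched. The coverage figures compare an interval in points with a target in percentages, which nobody would knowingly do, and they rest on assumed baselines. Section 6.2.1 does not state a unit, so points is an inference. If percentage change was meant throughout, an interval computed on that scale would have its stated coverage. Finally, an unadjusted change score is a valid estimator, so replacing it with ANCOVA goes beyond what a scale mislabel requires.

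Much of this stands. The superiority test is not damaged, the size of the shortfall depends on undocumented baselines, and ANCOVA is an option, not a necessity. The inconsistency remains. The calculation contains no division by baseline, and the powering is in points. Reading percentage change throughout only moves the error to the calculation sentence and cuts the result off from the 12-point basis for the sample size. Because this is the sole description of the primary analysis, its scale should not be left to the reader.

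**Conclusion.** The concern holds. As written, Section 6.2.1 makes a false statement about its primary interval, except in special cases such as zero effect with equal baselines. At the 12-point powering difference, the stated 95% becomes effectively 0% at SD 8 and about 0.01% to 30% at SD 22.7, for assumed common baselines of 30 to 50. Those figures depend on the assumed baselines and, for the second set, on an SD that the documents do not give; the mismatch of scales does not. That the intended unit is points is an inference, well supported by Sections 2.1 and 6.1. This should be corrected before analysis, but it does not invalidate the trial.

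**What to change.** Rewrite the calculation and coverage wording in Section 6.2.1 so that it names one estimator, the FJS, the two-year time point and the unit. Two versions would do:

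1. **Minimum correction, keeping the unadjusted change score.** State that the two-sided 95% interval is for the between-group difference in change from baseline in FJS points at two years. This restores the stated coverage and costs only wording.
2. **Baseline-adjusted alternative.** For example: *The primary endpoint is FJS at two years. The between-group difference in points will be estimated by ANCOVA of two-year FJS on treatment group and preoperative FJS, and reported with a two-sided 95% confidence interval for the adjusted mean difference.* This changes the estimator. It costs one degree of freedom and a small variance penalty for estimating the slope: the mean half-width is 0.6% wider (8.25 against 8.20) in the assumed case where it gains nothing.

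Neither version needs new data, visits or patients. On the PROMs, Section 3.10 says: "Each of these scores is completed preoperatively and then at regular intervals during follow-up". The preoperative case report form in Appendix 19.1 lists the FJS.

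Under either version, 12 points remains the powering difference and an aid to interpretation. Section 2 states "A superiority design will be used to evaluate whether FA TKA provides superior outcomes compared to MA TKA", so the interval does not have to clear 12, and the rewording should not introduce that as a success criterion.
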